9. TECHNICAL DETAILS

The SAP is subject to version control, and we anticipate modifications to analytic plans be documented herein. As in any study, the analytic plan may change due to assumption violations, logistical issues, unexpected empirical distributions of study outcomes, or a combination thereof. In these cases, the SAP will be updated accordingly. All analyses will be performed via SAS version 9.4 or higher (The SAS Institute; Cary, NC) or R version 3.6.0 or higher (The R Foundation for Statistical Computing platform). Table and figure formatting and style may be dictated by mode of dissemination or specific target journal(s) for results dissemination.

Summary of updates:

Version 2.0:

- 1) Removed reference to heterogeneity of treatment effects based on health literacy as these analyses will be outlined in a separate document.
- 2) Moved ABPM to exploratory analyses.
- 3) Updated target sample size based on interim analyses at request of the DSMB.
- 4) Updated modeling strategy overall to involve mixed modelling techniques (previously planned for ANCOVA at Week 12, only) to use both Week 6 and Week 12 data in analysis models. All longitudinal models will first explore a time-by-arm interaction term at the 5% level of significance in evaluating treatment effect.
- 5) Specified minor details on treatment of covariates in analyses.

- 6) Added in plans to explore potential strata combining study arm and add-on therapy.

10. TIMELINE FOR ANALYSES

As this is a phase II clinical trial, the original analysis plan did not include any formal interim statistical analyses involving hypothesis testing or any pre-specified stopping criteria for efficacy or futility on primary or secondary outcomes. Interim reports to the study team and data and safety monitoring board (DSMB) will consist of process measures such as protocol departures, missing values, missing forms, treatment regimen adherence, etc. and simple descriptive statistics on primary and safety outcomes of interest. In addition, weekly meetings with the study team will utilize central statistical monitoring techniques as a method of quality control and quality assurance for trial data on an ongoing basis. We foresee the DSMB requiring specific data listings or summarizations, but these will be specified at the time of the relevant DSMB meeting(s). At the request of the DSMB, we conducted an interim conditional power analysis, taking into consideration from both the QUARTET USA trial data as of August 2021 and further the QUARTET (Australia) results. These interim analyses, incorporating information to date, resulted in an updated recruitment target (and thus overall sample size goal). These interim analyses also resulted in the ultimate updates to the analytic strategy from an ANCOVA to one involving a mixed modeling approach to make use of both the six- and 12-week follow-up data for all participants. These modifications to the analytic plan resulted in an updated SAP (to version 2.0).

To preserve the integrity of the study, no formal final statistical analyses will occur until the REDCap database has been locked and all queries/discrepancies resolved; the date of database lock will be documented.

References:

1. Harris, P.A., et al., *Research electronic data capture (REDCap): a metadata-driven methodology and workflow process for providing translational research informatics support*. Journal of Biomedical Informatics, 2009. **42**(4): p. 377-381.
2. Scharfstein, D., et al., *Global sensitivity analysis for repeated measures studies with informative dropout: A fully parametric approach*. Statistics in Biopharmaceutical Research, 2014. **6**(4): p. 338-348.
3. Bahiru, E., et al., *Fixed-dose combination therapy for the prevention of atherosclerotic cardiovascular diseases*. Cochrane Database of Systematic Reviews, 2017(3).

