6. STATISTICAL METHODS

Descriptive statistics will summarize participant demographics and baseline clinical outcomes overall and across arms: proportion (percentages) for categorical variables; mean (\pm standard deviation) for continuous variables; and median (interquartile range) for skewed or count variables. Analyses in general will employ normal theory methods and residual diagnostics will evaluate validity of assumptions; where appropriate (i.e., in the event of low cell counts for categorical data or questions of normality), transformation of variables, nonparametric methods, or exact tests may be employed. All primary efficacy and safety analyses will be pre-specified as outlined in this SAP, and deviations from planned analyses or post hoc analyses will be labeled as such in any reports or dissemination materials.

Analyses will assume a two-sided 5% type I error rate unless otherwise specified; there will be some exploratory analyses that will involve a relaxed type I error rate (10%). There will be no corrections made for multiple hypothesis tests, as this is a phase II study evaluating preliminary efficacy.

Planned Primary, Secondary, Safety Analyses

The primary study analysis time point for all relevant outcomes is 12 weeks post randomization. The original analysis plan called for an analysis of covariance (ANCOVA), controlling for baseline value of each relevant outcome in addition to the following baseline covariates: sex, age at baseline, race/ethnicity, health literacy level (indicator of limited literacy as defined by the Newest Vital Sign instrument), and an indicator of monotherapy at baseline (vs. untreated). We deem these variables clinically relevant, important covariates; thus, all analyses will plan for adjustment for these covariates of interest (regardless of statistical significance in the current dataset) in evaluating efficacy of intervention in the present study. However, to better align with the analytic strategies of the QUARTET Australia study, and to make most efficient use of all follow-up data (both six-week and 12-week data), primary analyses will involve a linear mixed model with fixed study arm and baseline outcome value effects and a random participant effect to account for within-participant correlation. We Statistical Analysis Plan: February 9, 2022

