plan to conduct both unadjusted (for potential covariates mentioned above) and adjusted analyses. The updated details of these analyses are reserved for the statistical analysis plan. The basic analytic model will be as follows for each outcome (Y) for participant i ($i=1\dots N$) at visit j ($j=1, 2$; corresponding to Week 6 and Week 12):

$$Y_{ij} = \beta_0 + \beta_1 I(LDQT) + B_2(Y_{0i}) + B_3 visit + B_4(visit \times study\ arm) + b_i + e_{ij}$$

Under the assumption that error terms $e_{ij} \sim N(0, \sigma^2)$ is the random error term, $b_i \sim N(0, \sigma_b^2)$ is the participant-level random effect. If visit-by-study arm (B_4) is insignificant at the 5% level, we will remove that term from the model, and subsequently, we will further examine for an overall main effect for visit (B_3). If insignificant, we will also remove that effect from the model and evaluate intervention effect via the primary hypothesis test of interest:

$$H_0: \beta_1 = 0 \text{ vs. } H_1: \beta_1 \neq 0$$

for each outcome. However, if the visit-by-study arm interaction term or the visit term alone is significant, we will plan to evaluate the 12-week contrast via model-estimated least squared means as our primary analyses. All between-arm differences at both six- and 12-week time points will be reported as model-based estimates, corresponding 95% confidence limits, and p-value of the corresponding hypothesis test.

Secondary analyses (i.e., those for the secondary and exploratory outcomes of interest) will utilize data from all time points via (generalized) linear mixed modeling (GLMM) methods with the following specifications: identity, logit, or log link for continuous, binary, or count outcomes, respectively; fixed arm, visit, visit-by-arm interaction, and aforementioned covariates; and random participant effect. For secondary analyses, the model adjusted Wald type III tests for fixed effects will first evaluate significance of a visit-by-arm interaction at the 5% level of significance. If insignificant at the 5% level, then this interaction term will be removed and the model Wald type III test for fixed arm effect will evaluate the overall intervention effect in this longitudinal model at the 5% level.

The table below summarizes the general modeling strategy for each outcome. In each case, we plan to conduct both adjusted and unadjusted analyses. Adjusted analyses will include the aforementioned covariates.

Table: Modeling Strategy by Outcome

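### The primary model can report a pooled Week 6/12 effect as the Week-12 result, so a Week-12-specific contrast should always be shown beside it

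*SAP*

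**What the plan says.** SAP section 2 and Protocol 3.1 define the primary endpoint as the change in automated office SBP from baseline to 12 weeks.

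SAP section 10 records that "the original analysis plan did not include any formal interim statistical analyses involving hypothesis testing or any pre-specified stopping criteria". At the DSMB's request a conditional power analysis was then run on trial data to August 2021 together with the Australian results. Two consequences are stated. The first is the target: "These interim analyses, incorporating information to date, resulted in an updated recruitment target (and thus overall sample size goal". Section 8 gives the change as 365 to 87 randomized and 292 to 77 analysed. The second is the model: "These interim analyses also resulted in the ultimate updates to the analytic strategy from an ANCOVA to one involving a mixed modeling approach". Section 9 confirms that the earlier model was an ANCOVA at Week 12 only.

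The version 2.0 model in SAP section 6 (also Protocol 16.2) has terms for arm, baseline value, visit and visit-by-arm, plus a random participant effect. If the visit-by-arm term "is insignificant at the 5% level, we will remove that term from the model"; the visit term is examined next in the same way. The section also promises that "All between-arm differences at both six- and 12-week time points will be reported as model-based estimates". On error rates it says "Analyses will assume a two-sided 5% type I error rate unless otherwise specified" and "There will be no corrections made for multiple hypothesis tests, as this is a phase II study evaluating preliminary efficacy". The sensitivity analyses in section 7 are per protocol, multiple imputation and a global sensitivity analysis; the Week-12 ANCOVA is not among them.

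**The concern.** Once the visit-by-arm term is removed, the model contains a single arm effect. Its Week-6 and Week-12 differences are then the same number, averaged over both visits. The promise to report both visits does not separate them. Nor does the fallback to a least-squares-means contrast at Week 12 when only the visit term is significant, because that contrast is still the common arm effect.

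The endpoint is a 12-week quantity and the analysis first planned estimated it directly. Under version 2.0 a reader may see no estimate that uses Week 12 alone, and so could not check whether the conclusion depends on a model adopted after an interim analysis. The two visits could differ for a reason in the protocol itself: open-label amlodipine can be added from Week 6 (Protocol section 4), and SAP section 6 plans exploratory analyses in case the need for it differs by arm.

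**Working it through.** **1. The plan's own figures.** 365 × 0.80 = 292. 87 × 0.88 = 76.6, or 77. With 292 analysed, SD 15 and a 5 mmHg difference, SE = 15 × √(4/292) = 1.76 and power = Φ(5/1.76 − 1.96) ≈ 81%, which agrees with the stated 80%. ANCOVA with r = 0.5–0.6 gives 90.6–94.4%, matching the stated figure of over 90%. The conditional power of over 90% at the new target cannot be reproduced, because the interim n and inputs are not given.

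**2. What the model reports.** With visit-by-arm kept, the arm effect at visit j is β1 + B4·j, so the visits may differ. With it dropped, the effect is β1 at both visits. A retained visit term B3 is the same in both arms and cancels from the Week-12 contrast.

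**3. Precision at N = 77.** Inputs: SD 15 (SAP section 8) or 13 (baseline SD in the Australian trial, Protocol 2.3); r 0.5–0.6 (SAP section 8); residual correlation ρ between visits 0.4–0.6 (assumed); complete data and equal variance at the two visits (assumed).

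- Variance of one visit's contrast: v = 4 × SD² × (1 − r²)/77. Smallest: 4 × 169 × 0.64/77 = 5.62. Largest: 4 × 225 × 0.75/77 = 8.77.
- SE of the Week-12 contrast: √v = 2.4–3.0 mmHg.
- SE of the pooled effect: √(v(1 + ρ)/2) = 2.0–2.65 mmHg.
- SE of the difference in effect between visits: √(2v(1 − ρ)) = 2.1–3.2 mmHg.

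**4. Power of the pre-test.** For a true gap of 3 mmHg, z = 3/2.12 = 1.42 gives 29% power and z = 3/3.24 = 0.93 gives 15%. The interaction is missed in 71–85% of trials.

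**5. Bias and coverage.** Under these assumptions the pooled estimate is independent of the estimated gap, so the bias given a miss is half the gap: 1.5 mmHg for a 3 mmHg gap. Given significance, the Week-12 estimate is biased the other way, by −1.2 to −2.4 mmHg. Averaging over both branches: 0.71 × 1.5 + 0.29 × (−1.2) ≈ 0.7, and 0.85 × 1.5 + 0.15 × (−2.4) ≈ 0.9. By simulation, with a Week-12 effect of 6.9 mmHg (the Australian estimate):

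| Assumed excess at Week 6 (mmHg) | Interaction missed | Mean bias, all trials (mmHg) | Bias when missed (mmHg) | 95% CI coverage of Week-12 effect |
|---|---|---|---|---|
| 0 | 95% | 0 | 0 | 94% |
| 1 | 92–94% | 0.35 | 0.5 | about 94% |
| 3 | 71–85% | 0.7–0.9 | 1.5 | 89–91% |
| 5 | 34–66% | 0.5–1.1 | 2.5 | 85–90% |

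By symmetry, a larger effect at Week 12 would give an understatement of the same size.

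**6. The interim itself.** Suppose arm-level data drove the cut: 30–70 participants at the interim, a cut to 77 when conditional power on a favourable trend reached 90%, and otherwise continuation to between 100 and 292 analysed. All of these are assumed. Two-sided type I error is then about 5.2–5.9%. If arm-level data were not used, the interim leaves it at 5.0%.

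**The case against.** The redesign is openly disclosed in SAP sections 8, 9 and 10. Version 2.0 is dated February 2022, before the planned end of enrolment in May 2022 (Protocol section 25), and final analysis waits for database lock. All of that stands.

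A reader might infer that the mixed model was chosen because it looked better on the interim data. The documents do not support this. SAP sections 6, 9 and 10 all give the use of both follow-up visits as the purpose, and section 6 adds an outside reason, "to better align with the analytic strategies of the QUARTET Australia study".

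A reader might also blame the interim for the bias and poor coverage. That is wrong too: the figures in step 5 come from the dropping rule and would be the same had the mixed model been planned from the start.

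The visit gaps are assumed. The only longitudinal evidence in the documents, 6.9 mmHg at 12 weeks and 7.7 mmHg at 12 months in the Australian trial, shows no decline. With a gap of 1 mmHg the harm is slight.

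Finally, Week-12 reporting is partly covered. Baseline-adjusted Week-12 SBP is a listed secondary outcome, and the modelling table in section 6 refers to individual time points. But section 6 applies a dropping rule to secondary outcomes as well, and the table does not override it. The gap narrows but does not close.

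**Conclusion.** The concern holds in a limited form. Under the version 2.0 rule, a non-significant visit-by-arm test turns the reported Week-12 difference into a pooled Week 6/12 effect, and at 77 analysed that test detects a 3 mmHg gap only 15–29% of the time. The consequence depends on a gap that the documents neither show nor rule out: none if the visits agree, little at 1 mmHg, and coverage of 89–91% at 3 mmHg. These figures rest on the SD, correlation and complete-data assumptions in step 3.

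It would be tempting to go further and call the primary p-value and CI nominal in every case because the interim was unplanned. The documents do not support that. They do not say whether arm-level data informed the target or the model, and under the assumed rules the effect on type I error is at most about one percentage point. The label is warranted only if such data were used. The sentence on uncorrected multiple tests does not address this either way.

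**What to change.** **Main change, SAP section 6 and Protocol 16.2.** Keep the version 2.0 result as primary. Add that, whatever the p-values for visit-by-arm and visit, the baseline-adjusted Week-12 contrast with its 95% CI will be reported beside it. It can come from the mixed model with visit-by-arm retained or from the Week-12 ANCOVA first planned. Name one of the two now, so that no further choice is left open.

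**Secondary change, SAP section 10.** State whether arm-level data informed the change of target or of model. Describe the primary p-value and CI as nominal only if they did.

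**Cost.** One further analysis of data already collected, and a few sentences. The Week-12 contrast is less precise than the pooled effect (SE 2.4–3.0 against 2.0–2.65 mmHg), and the two results may differ, so the report must explain how they relate.
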